6.6.1. Ramucirumab Dose Adjustments, Delays, and Discontinuation

The ramucirumab dose may need to be delayed and/or reduced if the patient experiences an adverse event, including an adverse event of special interest (AESI) (Section [8.2.1.1.1](#)). Doses may be delayed to allow time for the patient to recover from the event. Certain AEs require immediate and permanent discontinuation of study treatment. Any patient who requires a dose reduction will continue to receive a reduced dose until discontinuation from ramucirumab or discontinuation from the study. Any patient who has had 2 dose reductions and who experiences a toxicity that would cause a third dose reduction must be discontinued from ramucirumab.

[Table JVDF.3](#) presents the ramucirumab dose reductions for each treatment cohort.

[Table JVDF.4](#) presents the criteria for dose modifications and dose discontinuations applicable if the patient experiences a ramucirumab AESI or other AEs at least possibly related to ramucirumab.

Table JVDF.3.

Ramucirumab Dose Reductions^a

	Dose Schedule 1: Gastric-GEJ/BTC (21-day Cycle)	Dose Schedule 2: Gastric-GEJ/NSCLC/Urothelial (21-day Cycle)
Starting dose	8 mg/kg on D1, D8	10 mg/kg on Day 1
First dose reduction	6 mg/kg on Day 1, Day 8	8 mg/kg on Day 1
Second dose reduction	5 mg/kg on Day 1, Day 8	6 mg/kg on Day 1

Abbreviations: BTC = biliary tract cancer; D = Day; GEJ = gastroesophageal; NSCLC = non-small cell lung cancer.

^a Ramucirumab dose reductions are allowed between cycles and within a given cycle.

Table JVDF.4. Dose-Modification Guidelines for Ramucirumab for Adverse Events at Least Possibly Related to Ramucirumab, including Adverse Events of Special Interest

Adverse Event NOTE: All Specific Adverse Events Listed are defined as AESIs in Section 8.2.1.1.1).		CTCAE Grade	Dose-Modification Guidelines NOTES: Dose reductions to occur as defined in Table JVDF.3. Treating physicians can modify or discontinue ramucirumab more conservatively than in the guidance below.
1.	Infusion-related reaction		
1.a.	Infusion-related reaction	2	
Interrupt and reduce the infusion rate by 50% for the duration of the infusion and for all future infusions.
 
Prior to all future infusions of ramucirumab, premedicate with:
 
 • an intravenous histamine H1 antagonist, such as diphenhydramine hydrochloride • dexamethasone or equivalent • acetaminophen/paracetamol

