13.b	Adverse Event	4	
Permanently discontinue treatment immediately, with the exception of Grade 4 fever or Grade 4 laboratory abnormality, in which case:
 
 • First occurrence: Delay ramucirumab until resolved to Grade 0-1. 
 ◦ If resolved to Grade 0-1, may resume ramucirumab original dose at the discretion of the investigator. ◦ If NOT resolved to Grade 0-1 within a reasonable timeframe, discontinue ramucirumab at investigator's discretion. • Second occurrence: Delay ramucirumab until resolved to Grade 0-1. 
 ◦ If resolved to Grade 0-1, reduce ramucirumab dose. ◦ If NOT resolved to Grade 0-1 within a reasonable timeframe, discontinue ramucirumab at investigator's discretion.

Dose-Modification Guidelines for Ramucirumab for Adverse Events at least Possibly Related to Ramucirumab, including Adverse Events of Special Interest (concluded)

Abbreviations: AESI = adverse event of special interest; CTCAE = Common Terminology Criteria for Adverse Events; NCI = National Cancer Institute.

- a Perform urinalysis within 3 days prior to each infusion of ramucirumab. If 24-hour urine collection is also performed, the results of 24-hour urine collection should be used for clinical decision-making.
- b Patients who enter the study with symptoms or laboratory values equivalent to NCI-CTCAE Version 4.0 Grade 1-2 adverse events should not necessarily have dose delays or reductions related to the persistence or mild worsening of those symptoms or laboratory values. Grade 2 toxicities which represent clinically significant worsening of symptoms from baseline, ramucirumab dose may be delayed at the discretion of the investigator. If the toxicity is resolved to Grade 0-1, may reduce ramucirumab dose. If the toxicity is not resolved to Grade 0-1, may discontinue ramucirumab.

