6.6.2. Pembrolizumab Dose Delays and Discontinuation

Adverse events (both nonserious and serious) associated with pembrolizumab exposure may represent an immunologic etiology. These AEs may occur shortly after the first dose or several months after the last dose of treatment. Pembrolizumab must be withheld (dose reductions are not permitted) for drug-related toxicities and severe or life-threatening AEs. See Section 6.9.1.3 for supportive care guidelines, including use of corticosteroids. [Table JVDF.5](#) presents the guidelines for treatment delays and discontinuation of pembrolizumab for specific AEs associated with pembrolizumab treatment.

Table JVDF.5. Pembrolizumab Treatment Discontinuation Guidelines for Specific Adverse Events at Least Possibly Related to Pembrolizumab

	Adverse Event	CTCAE Grade	Treatment Delay and Discontinuation
1	Diarrhea/Colitis	2-3	
Delay pembrolizumab until resolved to Grade 0-1.
 
 • If resolved to Grade 0-1 within 12 weeks of last dose, then resume pembrolizumab. • Within 12 weeks of last dose, if toxicity does not resolve to Grade 0-1 *or* with inability to reduce corticosteroid to ≤ 10 mg/day of prednisone or equivalent per within 12 weeks, discontinue pembrolizumab.
		4	Immediately and permanently discontinue pembrolizumab.
2	Increased AST, ALT, or Bilirubin^a	2	
Delay pembrolizumab until resolved to Grade 0-1.
 
 • If resolved to Grade 0-1 within 12 weeks of last dose, then resume pembrolizumab. • If NOT resolved to Grade 0-1 within 12 weeks of last dose, then discontinue pembrolizumab.
		3-4	Immediately and permanently discontinue pembrolizumab. See exceptions below.
3	Type 1 Diabetes Mellitus (if new onset) or Hyperglycemia associated with evidence of beta cell failure	T1DM or 3-4	
Delay pembrolizumab until patients are clinically and metabolically stable.
 
 • If clinically and metabolically within 12 weeks of last dose, then resume pembrolizumab. • If NOT clinically and metabolically stable within 12 weeks of last dose, then immediately and permanently discontinue pembrolizumab.

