4	Hypophysitis	2-4	
Delay pembrolizumab until resolved to Grade 0-1.
 
 • If resolved to Grade 0-1 within 12 weeks of last dose, then resume pembrolizumab. • Within 12 weeks of last dose, if toxicity does not resolve to Grade 0-1 *or* with inability to reduce corticosteroid to ≤ 10 mg/day of prednisone or equivalent per within 12 weeks, immediately and permanently discontinue pembrolizumab.

Pembrolizumab Treatment Discontinuation Guidelines for Specific Adverse Events at Least Possibly Related to Pembrolizumab (continued)

	Adverse Event	CTCAE Grade	Treatment Delay and Discontinuation
5	Hyperthyroidism	2	Therapy with pembrolizumab can be continued; non-selective beta-blockers (e.g., propranolol) are suggested as initial therapy for hyperthyroidism (Section 6.9.1.3.5).
		3	
Delay pembrolizumab until resolved to Grade 0-1.
 
 • If resolved to Grade 0-1 within 12 weeks of last dose, then resume pembrolizumab. • Within 12 weeks of last dose, if toxicity does not resolve to Grade 0-1 *or* with inability to reduce corticosteroid to ≤ 10 mg/day of prednisone or equivalent per within 12 weeks, immediately and permanently discontinue pembrolizumab.
		4	
 • Immediately and permanently discontinue pembrolizumab.
	Hypothyroidism	2-4	Therapy with pembrolizumab can be continued while treatment for the thyroid disorder is instituted.
6	Infusion Reaction	2	
 • First occurrence: Stop infusion of pembrolizumab until resolved to Grade 0-1. 
 ◦ If resolved to Grade 0-1 within 1 hour of stopping infusion, then restart infusion at 50% of the original rate (e.g., from 100 mL/hr to 50 mL/hr). ◦ If NOT resolved to Grade 0-1 within 1 hour of stopping infusion, delay pembrolizumab until symptoms resolve, and premedicate for the next scheduled dose. • Second occurrence: If toxicity develops despite premedication, immediately and permanently discontinue pembrolizumab.
		3-4	Immediately and permanently discontinue pembrolizumab.

Pembrolizumab Treatment Discontinuation Guidelines for Specific Adverse Events at Least Possibly Related to Pembrolizumab (continued)

	Adverse Event	CTCAE Grade	Treatment Delay and Discontinuation

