7	Pneumonitis	2	
Delay pembrolizumab until resolved to Grade 0-1.
 
 • If resolved to Grade 0-1 within 12 weeks of last dose, then resume pembrolizumab. 
Within 12 weeks of last dose, if toxicity does not resolve to Grade 0-1 *or* with inability to reduce corticosteroid to ≤ 10 mg/day of prednisone or equivalent per within 12 weeks, immediately and permanently discontinue pembrolizumab.

		3-4	Immediately and permanently discontinue pembrolizumab.
8	Renal Failure or Nephritis	2	
Delay pembrolizumab until resolved to Grade 0-1.
 
 • If resolved to Grade 0-1 within 12 weeks of last dose, then resume pembrolizumab. • Within 12 weeks of last dose, if toxicity does not resolve to Grade 0-1 *or* with inability to reduce corticosteroid to ≤ 10 mg/day of prednisone or equivalent per within 12 weeks, immediately and permanently discontinue pembrolizumab.
		3-4	Immediately and permanently discontinue pembrolizumab.
9	Other Adverse Events^b	3 or severe	
Delay pembrolizumab until resolved to Grade 0-1.
 
 • If resolved to Grade 0-1 within 12 weeks of last dose, then resume pembrolizumab. • Within 12 weeks of last dose, if toxicity does not resolve to Grade 0-1 *or* with inability to reduce corticosteroid to ≤ 10 mg/day of prednisone or equivalent per within 12 weeks, immediately and permanently discontinue pembrolizumab.
		4	Immediately and permanently discontinue pembrolizumab.

Pembrolizumab Treatment Discontinuation Guidelines for Specific Adverse Events at Least Possibly Related to Pembrolizumab (concluded)

Abbreviations: AE = adverse event; ALT = alanine aminotransferase; AST = aspartate aminotransferase; CTCAE = Common Terminology Criteria for Adverse Events; T1DM = type 1 diabetes mellitus.

Note: Permanently discontinue for any severe or Grade 3 drug-related AE that recurs or any life-threatening event. Reoccurrence of Grade 2 pneumonitis also warrants permanent discontinuation.

- a For patients with liver metastasis who begin treatment with Grade 2 AST or ALT, if AST or ALT increases by greater than or equal to 50% relative to baseline and lasts for at least 1 week, then patients should be discontinued.

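### The Note to Table JVDF.5 permanently stops pembrolizumab after a life-threatening event, three entries of the same table resume or continue it, and no precedence is stated

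*Protocol*

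**What the plan says.** **Pembrolizumab (Protocol 6.6.2).** The section text sets a general rule: "Pembrolizumab must be withheld (dose reductions are not permitted) for drug-related toxicities and severe or life-threatening AEs". The Note at the foot of Table JVDF.5 adds a second: "Permanently discontinue for any severe or Grade 3 drug-related AE that recurs or any life-threatening event". Neither exempts any row. Within the table:

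- Row 3, new-onset type 1 diabetes or Grade 3-4 hyperglycemia with beta cell failure: delay, then "If clinically and metabolically within 12 weeks of last dose, then resume pembrolizumab".
- Row 4, hypophysitis Grade 2-4: delay, then "If resolved to Grade 0-1 within 12 weeks of last dose, then resume pembrolizumab".
- Hypothyroidism Grade 2-4, listed under row 5: "Therapy with pembrolizumab can be continued while treatment for the thyroid disorder is instituted".

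**Ramucirumab (Protocol 6.6.1).** The text says "Any patient who requires a dose reduction will continue to receive a reduced dose until discontinuation from ramucirumab or discontinuation from the study". Table JVDF.4 line 13.b orders a permanent stop for other related Grade 4 events, with a written exception for fever and laboratory abnormalities. After a first such occurrence, "If resolved to Grade 0-1, may resume ramucirumab original dose at the discretion of the investigator". Lines 2.a and 3.a of the same table refer to the current dose instead, and Table JVDF.3 uses the term starting dose.

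**The concern.** A site that faces a life-threatening event in one of the three pembrolizumab categories has two written instructions that cannot both be followed, and nothing says which governs. These rules decide who stops and who is re-exposed in a trial whose primary objective is safety and tolerability.

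The choice also reaches the analysis. SAP 5.3.6 summarises infusions received, duration of treatment, delays and dose intensity, and SAP 5.3.8 lists adverse events that led to discontinuation. The same event could be recorded as a delay, as an uninterrupted course or as a permanent stop, depending on the sentence followed. The effect on disposition is weaker. Under Protocol 7.1 a patient has discontinued study treatment only when both drugs are stopped, so a patient who stops pembrolizumab alone need not appear there.

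The ramucirumab wording raises a smaller question, about dose level only: whether a patient already on a reduced dose could go back up after a first Grade 4 fever or laboratory abnormality.

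**Working it through.** The plan gives no figure to reproduce, so the check sets the passages side by side.

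**1. Entries in Table JVDF.5 that cover Grade 4**

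| Entry | Instruction at Grade 4 | Consistent with the Note if the event is life-threatening? |
|---|---|---|
| Diarrhea/colitis | permanent stop | yes |
| AST, ALT or bilirubin | permanent stop, with a pointer to exceptions | yes |
| Type 1 diabetes/hyperglycemia | delay, resume | **no** |
| Hypophysitis | delay, resume | **no** |
| Hyperthyroidism | permanent stop | yes |
| Hypothyroidism | continue | **no** |
| Infusion reaction | permanent stop | yes |
| Pneumonitis | permanent stop | yes |
| Renal failure/nephritis | permanent stop | yes |
| Other adverse events | permanent stop | yes |

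Count: 7 consistent + 3 not = 10.

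**2. Does the specific row simply beat the general Note?** The table does not support that as a rule. The Note's second sentence makes recurrent Grade 2 pneumonitis a permanent stop, while row 7 delays and resumes Grade 2 pneumonitis with no limit on recurrence. There the Note is meant to override a row. Where exceptions were intended they were written down (row 2 of Table JVDF.5, line 13.b of Table JVDF.4). No such wording protects rows 3, 4 or 5.

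**3. How far does the conflict extend?** The Note says life-threatening, not Grade 4, and the documents do not equate the two. Lines 2.a and 13.a of Table JVDF.4 label Grade 3 events as not life-threatening, and row 9 of Table JVDF.5 pairs Grade 3 with severe. Both suggest that Grade 4 is the life-threatening tier, but this is inference. The range is:

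- if every Grade 4 event counts as life-threatening, all Grade 4 events in the three entries are in conflict;
- if only some do, only those are in conflict.

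The overlap is realistic for row 3 at least, because the supportive-care text in 6.9.1.3.3 includes diabetic ketoacidosis in that category.

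**4. Hypothyroidism against the section text.** The 6.6.2 sentence requires a hold for severe as well as life-threatening events. The hypothyroidism entry requires none at any grade from 2 to 4. This second conflict does not depend on how Grade 4 is read.

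**5. Ramucirumab.** Seven entries in Table JVDF.4 name Grade 4: infusion reaction, hypertension, thromboembolic events, bleeding, heart failure, hypothyroidism and other events. None sets a permanent stop against continuation. The remaining tension is in line 13.b, first occurrence. It needs two conditions: the patient was reduced earlier (for example under line 3.c), and *original* means the starting dose. Only if both hold would the Table JVDF.3 doses give steps of 8/6 = 1.33 or 8/5 = 1.60 in Schedule 1, and 10/8 = 1.25 or 10/6 = 1.67 in Schedule 2. If *original* means the dose before the delay, there is no step and no conflict.

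**6. Size per cohort.** One patient is 1/25 = 4% or 1/15 = 6.7% of a Phase 1b cohort. This holds for any single patient and is not an estimate of frequency.

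**The case against.** The best defence of the pembrolizumab table is that it works in two layers. The rows give grade-based guidance, and the Note is an override for events that truly endanger life, a term that Protocol 8.2.1.2 glosses as imminent danger of death. The DLT definition and line 13.b also decline to treat every Grade 4 laboratory value as decisive. This defence stands in part. A reader might infer that the Note forbids every Grade 4 resumption in rows 3 to 5, and the documents do not support that. But the two-layer reading is itself an inference, and a reader who gives priority to the rows reaches the opposite result for the same life-threatening event.

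On recurrence, rows 3, 4 and 5 are silent, so the Note's recurrence clause mostly supplements them. That is a point to clarify and not a further contradiction.

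On ramucirumab the defence is strong. A reader might infer that both tables stop a patient under one sentence and continue the patient under another. The documents do not support this. Section 6.6.1 says only that certain events end treatment, line 13.b states its own exception, and the hypothyroidism line contradicts no general ramucirumab rule. The original-dose sentence is permissive, while the 6.6.1 sentence is mandatory. The heading of Table JVDF.4 allows physicians to be more conservative, so a site that keeps a reduced patient reduced breaches neither. Line 13.b also contrasts its first occurrence with a reduction at the second, which favours reading *original* as the dose before the delay. What remains is an undefined word.

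A reader might also infer that sites would certainly act in opposite ways. The documents do not show that. They give no incidence for these Grade 4 events on the combination. Sites must also report the circumstances of any reduction or discontinuation caused by an adverse event (Protocol 8.2.1), so divergence would be partly visible.

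**Conclusion.** The point holds for Table JVDF.5. Three of the ten entries that cover Grade 4 allow resumption or continuation where the Note, for a life-threatening event, orders a permanent stop, and no precedence is stated. The hypothyroidism entry also conflicts with the withholding sentence in 6.6.2. The conflict with the Note is confined to Grade 4 events that are life-threatening. How many that is depends on a definition the protocol does not give.

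For Table JVDF.4 only a secondary wording point holds. It applies to already reduced patients, and only if *original* is read as the starting dose. It is not a stop-versus-continue conflict.

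The number of patients affected is expected to be small. The reason to act is that stopping rules in a safety and tolerability trial should not contradict each other, and the correction is cheap. Nothing here implies a view on which clinical rule is right.

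**What to change.** Three wording changes, with the content decided by the sponsor's clinical team:

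1. Reconcile the Note to Table JVDF.5 and the withholding sentence of 6.6.2 with rows 3, 4 and 5 (hypothyroidism entry). State which takes precedence for each, including when an event recurs.
2. State what life-threatening means in the Note relative to CTCAE grade.
3. Reconcile *original dose* in Table JVDF.4 line 13.b with the reduction rule in 6.6.1, so that the instruction for an already reduced patient is unambiguous.

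The cost is amendment wording in 6.6.1, 6.6.2 and their two tables, and a letter to sites. No extra patients, visits or data are needed.

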6.6.3. Dose Delays for Reasons Not Related to Study Treatment

Dosing interruptions of either study drug are also permitted for reasons not related to study treatment (for example, elective surgery, unrelated medical events, patient vacation, and/or holidays).

Patients should resume the delayed study drug(s) within 21 days of the scheduled interruption, with every effort made to start on Day 1 of the next dosing schedule, unless otherwise discussed with the Sponsor. The reason for interruption should be documented on the case report form (CRF).

6.7. Treatment Compliance

The study medication will be administered only at the investigational sites by the authorized study personnel. As a result, treatment compliance is ensured.

During Phase 1a, DLT-evaluable population is defined as all enrolled patients in DLT Phase 1a who either completed 21 days of observation or discontinued study treatment or study participation before completing 1 cycle due to a DLT.

Any patient who discontinued from the study before completing safety monitoring for the 21-day DLT observation period for any other reason than a DLT will be considered non-evaluable for DLT assessment.

Patients who are not evaluable for pharmacokinetics, but who complete 1 cycle of therapy, may be replaced upon consultation with the investigator(s) and the Lilly CRP/CRS to ensure adequate PK data, unless accrual to that cohort has stopped due to a DLT.

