Abbreviations: C_{max} = maximum concentration; C_{min} = minimum concentration; DCR = disease control rate; DOR= duration of response; irRECIST= immune-related RECIST; ORR = objective response rate; OS = overall survival; PFS = progression-free survival; PK = pharmacokinetics; RECIST = Response Evaluation Criteria In Solid Tumors; SAEs = serious adverse events; TEAEs = treatment-emergent adverse events; TTR = time to response.

Treatment Arms and Duration:**DLT Phase 1a**

Patients will be treated for up to 21 days (1 cycle); patients without a DLT may continue in Expansion Phase 1b.

Dosing Schedules

- **Schedule 1:** ramucirumab 8 mg/kg on Day 1 and Day 8 and pembrolizumab 200 mg (fixed dose) on Day 1, in 3 patients with gastric-gastroesophageal (GEJ) cancer or biliary tract cancer (BTC)
- **Schedule 2:** ramucirumab 10 mg/kg and pembrolizumab 200 mg (fixed dose) on Day 1, in 3 patients with either gastric-GEJ, NSCLC, or urothelial cancer

Number of patients: up to 12 DLT-evaluable patients (up to 6 enrolled in each dosing schedule)

Expansion Phase 1b

Duration: Continues until approximately 2 years after the first patient received study treatment. Individual patients may continue treatment for up to 35 cycles (approximately 2 years), until confirmed progressive disease or discontinuation for any other reason.

Treatment Cohorts

- **Schedule 1 Dose:**
 - **Gastric-GEJ (2nd - 3rd Line) Cohort A (15 patients),**
 - **BTC (2nd - 3rd Line) Cohort A1 (25 patients), and**
 - **Gastric-GEJ (1st Line) Cohort A2 (25 patients).**
- **Schedule 2 Dose:**
 - **Gastric-GEJ (2nd - 3rd Line) Cohort B (15 patients),**
 - **NSCLC (2nd - 4th Line) Cohort C (25 patients),**
 - **Urothelial (2nd - 4th Line) Cohort D (25 patients), and**
 - **NSCLC (1st Line) Cohort E (25 patients).**

Number of patients: approximately 155 patients

Statistical Analysis:

For the Phase 1a, a 3+3 design will be used to assess the safety of ramucirumab in combination with pembrolizumab. Additional patients will be enrolled in a dosing schedule to achieve the minimum of 3 evaluable patients, if dropouts or dose interruptions or reductions occur that result in a patient being non-evaluable for DLTs. Data will be reviewed by dose schedule group (3 patients).

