6.1.1.1. Phase 1a: Dose-Limiting Toxicity Observation

For the 21-day Phase 1a DLT observation period, the following criteria will be used to determine the progress of the study:

- If none of the initial 3 patients within a dose schedule develops a DLT, Expansion Phase 1b will start.
- If 1 of the initial 3 patients within a dose schedule develops a DLT, 3 additional patients will be added.
- If ≤ 1 of 6 patients within a dose schedule develops a DLT, Expansion Phase 1b will start.
- If 2 or more patients develop a DLT, enrollment will stop and an alternative dose level may be considered (in which case the protocol would be amended).

No intra-patient dose escalation or reduction is allowed during DLT observation. For the purpose of patient management, DLTs will lead to dose interruption during the observation period. Dose modifications will be allowed after the observation period.

For either group, if dropouts, dose interruptions, or reductions occur that result in a patient being nonevaluable for DLTs (“evaluable” is defined in Section 6.7), additional patients will be enrolled to achieve the minimum of 3 evaluable patients. The need for patient replacement will be determined based on consultation with the investigator and Lilly CRP/clinical research scientist (CRS). Patients who withdraw from the study during the DLT period for reasons other than a DLT may be replaced within the same dose level.

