6.6. Dose Adjustments, Delays, and Discontinuation

Doses of either study drug may need to be delayed, reduced (ramucirumab only), or discontinued to manage specific AEs or other toxicities.

When a study drug is delayed, if possible and appropriate, patients should resume study treatment within 21 days, with every effort made to start on Day 1 of the next dosing schedule.

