Gastroesophageal Junction Adenocarcinoma, Non-Small
Cell Lung Cancer, Transitional Cell Carcinoma of the
Urothelium, or Biliary Tract Cancer**

Overview

Protocol I4T-MC-JVDF, An Open-Label, Multicenter, Phase 1 Study of Ramucirumab plus Pembrolizumab in Patients with Locally Advanced and Unresectable or Metastatic Gastric or Gastroesophageal Junction Adenocarcinoma, Non-Small Cell Lung Cancer, or Transitional Cell Carcinoma of the Urothelium, has been amended. The new protocol is indicated by amendment (b) and will be used to conduct the study in place of any preceding version of the protocol.

The overall changes and rationale for the changes made to this protocol are as follows:

- Addition of title, rationale, study design, entry criteria, study procedures and statistical elements for 3 new Phase 1b expansion Cohorts, to include first-line Gastric-GEJ (Schedule 1), first-line NSCLC patients (Schedule 2), and second or third line BTC patients (Schedule 1). At the time of this amendment, Phase 1A Schedule 1 DLT observation is ongoing; Phase 1A Schedule 2 DLT observation has been completed. For first line Gastric/GEJ and first line NSCLC patients, more frequent tumor imaging schedule (every 4 weeks for the first 12 weeks) is required to monitor anti-tumor response to study treatment and initiate alternative treatment as determined by treating investigators.
- Clarifications and refinements, as follows:
 - The final analysis of safety and preliminary efficacy will occur approximately 2 years after the first patient received first study treatment. Separate interim analyses will occur after all patients in each cohort have completed approximately 24 weeks of study treatment or discontinued for any reason. Safety and preliminary efficacy will be analyzed separately for each cohort.
Rationale: This change was implemented to harmonize the interim analysis and final analysis with the intent of the trial design. There is no change to the study treatment duration for each individual patient (35 cycles, approximately 2 years).
 - In Inclusion Criterion [20], clarified that baseline tumor tissue samples must be evaluable, and elaborated on guidance regarding the submission of tumor tissue samples in Section 8.4.2.

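### Protocol 6.7 sets no Cycle 1 dose requirement for DLT evaluability, so a patient who missed planned dosing, such as Day 8 ramucirumab, counts towards the three

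*Protocol*

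**What the plan says.** Protocol 6.7 makes evaluable every Phase 1a patient "who either completed 21 days of observation or discontinued study treatment or study participation before completing 1 cycle due to a DLT". The one group it calls nonevaluable is "Any patient who discontinued from the study before completing safety monitoring for the 21-day DLT observation period for any other reason than a DLT". Neither sentence mentions doses received.

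Protocol 6.1.1.1 enrolls additional patients, up to a minimum of three evaluable, "if dropouts, dose interruptions, or reductions occur that result in a patient being nonevaluable for DLTs", and points to 6.7 for what evaluable means. The synopsis and Section 9.2 carry the same rule: "if dropouts or dose interruptions or reductions occur that result in a patient being non-evaluable for DLTs". On replacement, 6.1.1.1 adds: "The need for patient replacement will be determined based on consultation with the investigator" and the sponsor's physician or scientist.

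On missed doses, 6.6.3 says: "Dosing interruptions of either study drug are also permitted for reasons not related to study treatment". It states no exception for the DLT period. Section 6.6 says that after a delay, where possible and appropriate, "patients should resume study treatment within 21 days, with every effort made to start on Day 1 of the next dosing schedule".

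The SAP uses the term DLT-evaluable in 5.1.1, but its analysis populations in 5.2.1.7 include no such set.

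The amendment (b) summary in Attachment 9 gives the status at that time: "Phase 1A Schedule 1 DLT observation is ongoing; Phase 1A Schedule 2 DLT observation has been completed".

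**The concern.** Three places in the protocol intend that inadequate dosing can disqualify a patient from the DLT count. The section they rely on for the definition contains no dosing test, so that intention has nothing to act on. Interruptions cannot simply mean interruptions that end in withdrawal, because dropouts are listed separately. Nor can they mean interruptions caused by a DLT, because such a patient counts as a DLT and is not nonevaluable.

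The gap matters most in Schedule 1, where Day 8 supplies half of the Cycle 1 ramucirumab and is what distinguishes the schedule. A patient without it has not tested the regimen, yet can be one of three DLT-free patients on whom 6.1.1.1 opens expansion. Schedule 1 feeds Cohorts A, A1 and A2: 15 + 25 + 25 = 65 patients.

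The mismatch is not confined to Schedule 1. A Day 1 infusion in either schedule can be stopped for a Grade 3-4 infusion reaction (Tables JVDF.4 and JVDF.5). Under 6.1.1.1.1 a reaction during infusion is not a DLT, so that patient too is evaluable after 21 days, whatever fraction was infused.

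**Working it through.** **Dose.** The SAP (5.2.1.2) plans 5.3 mg/kg/week of ramucirumab for Schedule 1 and 3.3 for Schedule 2. These reproduce: (8 + 8)/3 = 5.33 and 10/3 = 3.33. Without Day 8, a Schedule 1 patient receives 8/3 = 2.67 mg/kg/week. That is 8/16 = 50% of the Schedule 1 plan and 2.67/3.33 = 80% of the Schedule 2 plan.

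**Decision rule (6.1.1.1).** The schedule opens with 0 DLTs in 3 patients, or with 1 in 3 followed by 0 in the next 3.

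**Assumptions.** The documents give no DLT rate, so the full-dose rate p is varied from 20% to 50%. The under-dosed patient's risk is r = f × p with f = 0.5 or 0.75. The direction has some support in 4.2.1.1: in RAINBOW, higher ramucirumab exposure went with more Grade 3 or greater hypertension, neutropenia and leukopenia. In REGARD no such relationship was identified for hypertension or neutropenia, which had low incidence. The size of f is an assumption. Any second group of three is taken as fully dosed.

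**Formulas**, with q = 1 − p:

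- Three fully dosed patients: P(open) = q³ + 3pq² × q³
- One under-dosed among the first three: P(open) = (1 − r)q² + [r q² + (1 − r) × 2pq] × q³
- Difference = (1 − f) × p × [q² − (q² − 2pq) × q³]

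**Example, p = 0.20, f = 0.5 (r = 0.10).** Fully dosed: 0.512 + 0.384 × 0.512 = 0.709. One under-dosed: 0.9 × 0.64 + (0.1 × 0.64 + 0.9 × 0.32) × 0.512 = 0.576 + 0.352 × 0.512 = 0.756. The gain is 4.8 points before rounding.

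| Full-dose DLT rate p | All three fully dosed | One at 0.5 of the risk | Gain (points) | One at 0.75 of the risk | Gain (points) |
|---|---|---|---|---|---|
| 0.20 | 0.709 | 0.756 | 4.8 | 0.732 | 2.4 |
| 0.33 | 0.434 | 0.508 | 7.4 | 0.471 | 3.7 |
| 0.40 | 0.309 | 0.386 | 7.7 | 0.348 | 3.9 |
| 0.50 | 0.172 | 0.242 | 7.0 | 0.207 | 3.5 |

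The figures are for one such patient among the first three and for the count alone, before any clinical review.

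**The case against.** **An omitted Day 8 is not certain to arise.** A reader might infer that 6.6.3 plainly permits a skipped Day 8 in the DLT window and that it is never made up. The documents do not settle either point. Section 6.1.1.1 places dose modifications after the observation period, and SAP 5.3.6 counts a delay as a modification. Section 6.6.3 lets resumption be discussed otherwise with the sponsor, and the treatment column in Attachment 1 carries a ±7-day window, so a late Day 8 within Cycle 1 is not excluded. This stands as a limit: the omission is possible, not established. It does not remove the gap, because 6.1.1.1 itself foresees interruptions during this period.

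**Discretion may catch it.** Three is a minimum, replacement is discussed between investigator and sponsor, a documented safety review follows the three patients, and the decision to expand rests on all the data (9.8). With at most six evaluable patients per schedule, a missed infusion would probably be seen. That also stands. But seeing it is not a rule for acting on it: no written criterion says when to replace, and by 6.7 the patient already belongs to the three.

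**A dose withheld for a DLT changes nothing.** That is correct. Such a patient is counted as a DLT, and the point concerns misses without one.

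**Conclusion.** The inconsistency holds on the text. Section 6.7 counts an under-dosed, DLT-free patient whom the synopsis, 6.1.1.1 and 9.2 mean to be able to exclude, and the SAP does not resolve it. The error favors opening the schedule if lower exposure carries lower DLT risk. Given one such patient among the first three, the chance of opening rises by about 5 to 8 points at half the full-dose risk and about 2 to 4 points at 0.75 of it, for full-dose DLT rates of 20% to 50%. The risk ratio is assumed. The frequency of missed doses is not given, so no overall effect on the trial can be claimed.

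A reader might infer a rise of about 10 to 15 points by comparing a patient already known to be DLT-free with a replacement whose outcome is unknown. That is the formula at f = 0, twice the half-risk gain. A fully dosed patient known to be DLT-free would give the same difference, so it measures knowledge of the outcome and not the missed dose. Seen in advance, it assigns no DLT risk to someone who had 8 mg/kg of ramucirumab, the full pembrolizumab dose and 21 days of observation.

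For the same reason, it is too strong to say that the zero-DLT one-sided 95% upper bound moves from 1 − 0.05^(1/3) = 63% with three patients to 1 − 0.05^(1/2) = 78% with two. That gives the under-dosed patient no weight at all.

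This is a clarification worth making, not a defect that invalidates Phase 1a.

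**What to change.** Add a dosing condition to protocol 6.7 for both schedules, along these lines:

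> A patient without a DLT is DLT-evaluable only if all planned Cycle 1 infusions were given and the 21-day observation was completed. For Schedule 1 these are ramucirumab on Day 1 and on Day 8 within the visit window, and pembrolizumab on Day 1. For Schedule 2 they are both Day 1 infusions. A partial infusion counts as given if at least [stated fraction] of the planned dose was received. Any other patient without a DLT is nonevaluable and is replaced. If a dose was withheld for related toxicity, the decision under DLT criterion 4 is documented before replacement.

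Define the same set in SAP 5.2.1.7. List replaced patients with the reason beside the DLT listing, so that replacement cannot hide a toxicity. Check the Cycle 1 dosing records of Phase 1a patients already observed in both schedules, including Schedule 2, which had finished at amendment (b). The DLT criteria need no change.

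The cost is a few sentences in two documents, a short record check, and occasionally one more Phase 1a patient with a further 21-day observation, which the plan already allows for.
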